11.2. ANALYSIS POPULATIONS

It is expected during this clinical investigation only one population for ReUnion RSA System will exist and all subjects will be analyzed “Per Protocol” (PP). However, it cannot be fully avoided that in theory subjects might need to be excluded from the PP population. In this occasion, there will be two groups being fully analyzed to ensure transparency and avoid bias.

The groups are defined as follows:

- Intent-to Treat Population**

The Intent-to-Treat (ITT) Population is defined to be all enrolled subjects. An enrolled subject is a subject that has signed informed consent, all screening procedures have been successfully completed, is eligible and can receive treatment. The ITT population will not be analyzed for the annual reports and will only be included in the final report.

- **Per Protocol Population**

The PP Population is defined to be all subjects in the ITT Population with no major protocol violations. The protocol deviations that will exclude a subject are as follows:

- The subject does not receive the ReUnion RSA System
- The subject does not meet all eligibility criteria
- The subject has a protocol deviation that is considered likely to affect subject outcomes.

After the clinical investigation has been completed, a review of the data will be conducted to determine which subjects are to be excluded from the PP population.

11.3. ANALYSIS AND EVALUATION

11.3.1. Statistical Analysis

Evaluation elements are defined as the questions on the CRF/eCRF. The SAP lists all evaluation elements and secondary elements which will be based on calculations between two or more evaluation elements.

All quantitative variables, including those based on calculations (secondary elements), will be analyzed with a case summary evaluation before the detailed characteristics and parameters can be evaluated. A case summary contains a listing of the number of valid cases/values, missing cases/values (if any) and total cases/values in the specific analysis. In general, as central position parameter for quantitative variables the mean, median and mode will be analyzed. As variation parameter the standard deviation, 95% confidence interval of the mean, interquartile range and range (based on maximum and minimum) will be calculated. All quantitative variables will be assessed for normality using the Shapiro-Wilk test. For optional visualization of quantitative variables, box-and-whisker plots will be used. Additional analyses like skewness and kurtosis measures or standard errors also are optional.

All qualitative variables, including those based on summaries (secondary elements), will be analyzed listing the proportions, frequencies, column and row totals, and missing proportion, if any.

The SAP reflects this approach and specifies the variables characteristics (quantitative or qualitative) in detail together with the related analysis strategy. This also includes calculation and summaries based on primary elements and the required analysis.

11.3.2. Primary Analysis / Endpoint

The objective of the clinical investigation is to demonstrate the non-inferiority (equal or better) of the ASES Shoulder Score in relationship to the officially cleared indications in comparison to respective clinical outcome data in the scientific literature.

[figure not shown]
Data collection of ASES Shoulder Score will start pre-operatively and will be collected according to schedule in Table 1. This will be repeated annually in all subjects who have the prosthesis with full or partial implant survival (including all subjects without removal of all endo-prosthesis components).

The 24 months post-operative results for subjects implanted with ReUnion RSA System will be compared to a historical group and results reported by respective clinical outcome data in the scientific literature. The benchmark sources and values will serve as the control group for the ReUnion RSA System subjects.

Higher ASES Shoulder Score results are linked to better subject results and vice versa.

The clinical investigation endpoint is non-inferiority to the control, meaning the clinical investigation result should be equal or better than the control. In this clinical investigation, an equal or better ASES score result means equal or more (\geq). As only results from samples will be captured, results are mostly estimates of the true population parameter. These estimates vary by a certain area, where it is expected that the true population parameter falls within. Based on this, it is required to specify a lower limit for the acceptable difference or zone of indifference, denoted as $-\theta$.

Hypotheses are developed to allow for a comparison of the 24 months post-operative ASES score effectiveness / performance between the two underlying populations. The 24 months post-operative ASES Shoulder Score is the primary endpoint of this clinical investigation. Hypothesis tests will be one-sided with a significance level α of 5%.

Hypothesis	Equations	Interpretation
Null (H_0)	$A - B < -\theta$	Central tendency of A is inferior to the central tendency of B.
	ReUnion RSA System – Control (Benchmark) $< -\theta$	
Alternative (H_1)	$A - B \geq -\theta$	Central tendency of A is non-inferior to the central tendency of B.
	ReUnion RSA System – Control (Benchmark) $\geq -\theta$	
		
Possible Evidence (p)	Possible Decisions	Possible Conclusions – ASES score
p-value $> \alpha$ (0.05)	Fail to reject null hypothesis (H_0)	ReUnion RSA System $<$ Control (Benchmark) Insufficient evidence to reject the null hypothesis ($H_0: A - B < -\theta$) at the pre-determined significance level of 5%.
p-value $\leq \alpha$ (0.05)	Reject null hypothesis (H_1)	ReUnion RSA System \geq Control (Benchmark) Sufficient evidence to reject the null hypothesis ($H_0: A - B < -\theta$) at the pre-determined significance level of 5%.

To test non-inferiority, the 24 months mean ASES Shoulder Score result of the ReUnion RSA System group will be compared to the mean estimate of the control group (71.27 points).

To be able to identify an acceptable difference or zone of indifference ($-\theta$), the pooled standard deviation of the ASES Shoulder Score result at 24 months post-operative in the control group (Benchmark) was used as lower limit (pooled standard deviation of control is 19.40 points).

The lower maximum acceptable difference ($-\theta$) is 51.87 points (mean of control - θ or $71.27 - 19.40 = 51.87$ points).

Based on the underlying distribution of the data and the result of the normality assessment, either the parametric one-sample t-test or the non-parametric one-sample sign test will be used to compare the 24 months post-operative ASES Shoulder Score results of the ReUnion RSA System against the value of 51.87 points.

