11.1. DETERMINATION OF SAMPLE SIZE

The determination of sample size is based on benchmark sources and values. To account for an estimated appropriate overall drop-out rate, Stryker intends to enroll the calculated number of subjects, multiplied by the number of cleared indications to reflect the underlying subject population adequately. For details, please see Table 2.

Benchmark and Objectives for Clinical Investigation

Endpoint	The non-inferiority (equal or better) of the ASES Score in relationship to the officially cleared indications in comparison to respective clinical outcome data in the scientific literature.			
Estimated drop-out rate	56% (confirmed by Medical Expert, see Cuff et al. [1])			
Benchmark Sources & Values ASES [points]				
Source	No.	n	Mean	Std. Dev.
No.	Title			Comments No.
1	Nolan et al. [2] 2011	71	76.1	NA
2	Naveed et al. [3] 2011	49	65	NA
3	Kelly 2 nd et al. [4] 2012	30	71.8	12.7
4	Patel et al. [5] 2012	28	66.2	21.3
5	Cuff et al. [6] 2012	76	75	NA
6a	Wiater et al. [7] 2014	37	84.9	18.9
6b	Wiater et al. [7] 2014	64	77.1	18.3
7a	Black et al. [8] 2014	33	74	23.8
7b	Black et al. [8] 2014	32	69.7	18
8a	Poon et al. [9] 2014	27	70	NA
8b	Poon et al. [9] 2014	23	68	NA
9	Kiet et al. [10] 2015	53	77	19
10	Steen et al. [11] 2015	24	79.9	20.2
11	Wagner et al. [12] 2015	154	65.0	NA
12a	Crosby et al. [13] 2017	73	55	25
12b	Crosby et al. [13] 2017	29	68	20
13	Vourazeris et al. [14] 2017	86	77.7	NA
14a	Otto et al. [15] 2017	32	58.6	NA
14b	Otto et al. [15] 2017	35	40.8	NA
15a	Mollon et al. [16] 2017	428	84.1	17.1
15b	Mollon et al. [16] 2017	48	78.1	21.8
16	Holschen et al. [17] 2017	44	65.3	20.9
17a	Friedmann et al. [18] 2017	340	86.7	15.8
17b	Friedmann et al. [18] 2017	251	82.1	18.2
18	Williams et al. [19] 2017	17	65.6	NA
Identified Cleared Indications				
No.	Indication			
1	Gross rotator cuff deficiency			
2	Degenerative arthritis			
3	Rheumatoid arthritis			
4	Revision of previously failed shoulder joint replacement			
Explorative Meta-Analysis - ASES (single group)				
Acceptance Criteria				
Confidence Interval (CI)				0.95 (95%) two-sided
Software Used				IBM SPSS V20

Case Processing Summary						
	Cases					
	Valid		Missing		Total	
	N	Percent	N	Percent	N	Percent
Mean ASES ReUnion_RSA_CER	25	100,0%	0	0,0%	25	100,0%
Std.Dev. ASES ReUnion_RSA_CER	15	60,0%	10	40,0%	25	100,0%

Descriptives						
Mean ASES ReUnion_RSA_CER						Statistic
Mean						71,2680
95% Confidence Interval for Mean						Lower Bound Upper Bound
						67,0288 75,5072

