Median						71,8000
Std. Deviation						10,26985
Minimum						40,80
Maximum						86,70
Interquartile Range						12,45
Std.Dev. ASES ReUnion_RSA_CER						Statistic
Mean						19,4000
95% Confidence Interval for Mean						Lower Bound Upper Bound
						17,7028 21,0972
Median						19,0000
Variance						9,393
Std. Deviation						3,06478
Minimum						12,70
Maximum						25,00
Interquartile Range						3,30

	
Red line: Pooled mean ASES Blue lines: 95% CI of pooled mean ASES Black line: Pooled median pooled ASES Box: Interquartile Range Green Line: Pooled mean ASES minus pooled std. dev. ASES (19.40) $71.27 - 19.40 = 51.87$ points

--	-------------------------------------------------------------------------------------------------------------------------------------------------------------------------------------------------------------------------------------------------------------------------------------------------------------

[figure not shown]
Acceptance Criteria for Sample Size Calculation	
Significance Level (α)	0.05 (5%)
Power (1- β)	0.80 (80%)
Confidence Interval (CI)	0.95 (95%)
Tails	2
Path	Non-inferiority – ReUnion RSA (A) \geq Benchmark (B, explorative meta-analysis in this document)
Hypotheses Pair	Null (H_0)
	Alternative (H_1)
Benchmark Timepoint	24 months post-operative

Benchmark n	25
Benchmark Mean	71.27 (pooled mean ASES [points])
Benchmark Std. Dev.	19.40 (pooled std. dev. ASES [points])
Benchmark Value Non-Inferiority Margin (-θ)	Pooled mean ASES minus pooled std. dev. ASES (19.40) 71.27 – 19.40 = 51.87 points
Software Used	IBM SPSS Sample Power V3.0

IBM SPSS Sample Power Output

One goal of the proposed clinical investigation is to test the null hypothesis that the population mean is 71.27 points. The criterion for significance (alpha) has been set at 0.05. The test is 2-tailed, which means that effects in both directions will be interpreted. With the proposed sample size of 10 cases, the clinical investigation will have power of 80.3% to yield a statistically significant result. This computation assumes that the population from which the sample will be drawn has a mean of 71.27 points with a standard deviation of 19.40 points. The observed value will be tested against a theoretical value (constant, non-inferiority margin) of 51.87 points.

IBM SPSS Sample Power Output – Screenshot

Estimated overall drop-out rate is 56% which leads to the requirement of enrolling additional 6 subjects into the clinical investigation.

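### The primary test is against 51.87, but its decision table words the result as ReUnion at or above, or below, a control of 71.27

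*Protocol*

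**What the plan says.** Protocol 11.3.2 defines the aim in two steps: "The clinical investigation endpoint is non-inferiority to the control, meaning the clinical investigation result should be equal or better than the control", and then "In this clinical investigation, an equal or better ASES score result means equal or more". The control mean is given as 71.27 points. The hypotheses are H0: A − B < −θ and H1: A − B ≥ −θ, and the table reads H1 as "Central tendency of A is non-inferior to the central tendency of B". The test, a one-sample t-test or sign test depending on the normality assessment, compares the "Score results of the ReUnion RSA System against the value of 51.87 points". It is one-sided at 5%.

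The decision table below the hypotheses gives the conclusions. For p ≤ 0.05 the cell begins with ReUnion ≥ and continues "Control (Benchmark) Sufficient evidence to reject the null hypothesis". For p > 0.05 it begins with ReUnion < Control, followed by a sentence that there is insufficient evidence to reject H0. Neither label carries −θ.

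SAP 3.1.1 (Table 3.1.1) repeats the text and the table. Protocol Table 2 describes the endpoint as "The non-inferiority (equal or better) of the ASES Score in relationship to the officially cleared indications" and gives the path as ReUnion ≥ Benchmark; SAP Table 3.2 does the same. The sample-size text says "The observed value will be tested against a theoretical value (constant, non-inferiority margin) of 51.87 points". SAP 6.6 specifies the same test without the two labels.

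**The concern.** A non-inferiority test against 51.87 answers one question: is the score more than 19.40 points below the benchmark? The two labels answer a different one, namely whether ReUnion is at or above the benchmark or below it. The hypothesis table and the second sentence of each conclusion cell are correct, so the decision table contradicts itself.

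These cells sit under the heading for possible conclusions on the ASES score, so they are the natural source for the report's wording of the primary result. A report that follows them could claim performance equal to or better than the literature although the only test was against a value 19.40 points lower. Conversely, a failed test would be reported as the device being worse than control, which a non-significant result cannot show.

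There is a notation slip in the same sections. 51.87 is called −θ and the non-inferiority margin, but by the plan's own arithmetic (71.27 − 19.40 = 51.87) θ is 19.40 and 51.87 is the threshold. This does not alter the test.

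**Working it through.** **Inputs.** Benchmark mean 71.27, SD 19.40 and threshold 51.87 (Protocol 11.1 and 11.3.2); one-sided α = 0.05 (11.3.2); enrolment 80 and drop-out 56% (11.1). The benchmark's own 95% confidence interval is printed in Table 2 as "67,0288 75,5072", that is 67.03 to 75.51. The number of subjects with a 24-month score is not given, so I take two ends: n = 80 × 0.44 ≈ 35 (all drop-out has occurred by 24 months) and n = 80 (none).

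**Reproducing the plan's figure.** d = (71.27 − 51.87)/19.40 = 1.0. A two-sided 5% one-sample t-test with n = 10 has power 80.31%, against the stated 80.3%. So the plan's power figure is also for the test against 51.87.

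**Formulas**, with SE = 19.40/√n:
- Lowest observed mean that passes: 51.87 + t(0.95, n−1) × SE
- 95% interval wholly below 71.27 if the mean is under: 71.27 − t(0.975, n−1) × SE
- Same against 67.03: 67.03 − t(0.975, n−1) × SE
- Mean needed in a one-sided 5% test against 71.27 itself: 71.27 + t(0.95, n−1) × SE

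| | n = 35 | n = 80 |
|---|---|---|
| SE | 3.279 | 2.169 |
| t(0.95), t(0.975) | 1.691, 2.032 | 1.664, 1.990 |
| Lowest passing mean | 57.41 | 55.48 |
| Interval below 71.27 if mean under | 64.61 | 66.95 |
| Interval below 67.03 if mean under | 60.37 | 62.71 |
| Needed against 71.27 itself | 76.81 | 74.88 |

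The lowest passing mean is 71.27 − 57.41 = 13.9 points (n = 35) or 71.27 − 55.48 = 15.8 points (n = 80) below the benchmark. Between rows 3 and 4 the label says ≥ Control while the interval lies wholly below control.

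**How often that conflict arises.** Probability that p ≤ 0.05 and the upper 95% limit is below 71.27 (normal data, SD 19.40, integrating over the sample SD):

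| True mean | n = 35 | n = 80 |
|---|---|---|
| 60 | 0.700 | 0.980 |
| 65 | 0.448 | 0.815 |
| 67.03 | 0.239 | 0.488 |
| 71.27 | 0.025 | 0.025 |

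**Sensitivity to SD** (smallest and largest study SDs in Table 2, 12.7 and 25.0). The window against 71.27 is 55.5–66.9 and 59.0–62.7 at n = 35, and 54.2–68.4 and 56.5–65.7 at n = 80. It never closes. Against 67.03 it closes at n = 35 with SD 25.0, where the limit 58.4 falls below the passing mean 59.0. At SD 19.40 the 71.27 window is empty at n = 10 (63.12 against 57.39) and just open at n = 16 (60.37 against 60.93).

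**The < Control label.** At SD 19.40 the highest upper 95% limit a non-significant mean can have is 51.87 + [t(0.95) + t(0.975)] × SE: 64.1 (n = 35), 59.8 (n = 80), 77.0 (n = 10). At the expected n the label therefore does not conflict with the interval, although non-rejection still does not establish it. At n = 10 it can conflict.

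**Sign test.** If normality is rejected, the test concerns the median, and the windows above do not apply. At n = 35, 23 subjects above 51.87 suffice (one-sided binomial p = 0.045), wherever those scores lie relative to 71.27.

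**The case against.** The strongest reply is that the label is never read alone. The same section explains that estimates vary and that a zone of indifference is therefore needed. The hypothesis rows carry −θ, each cell restates H0 correctly, and 71.27, 19.40 and 51.87 are all printed openly. SAP 6.6 has no such label. All this is true, and it means a careful reader can see the conflict. But the zone-of-indifference sentence motivates the margin; it does not redefine ≥ Control, and the sentences before it define equal or better as equal or more. A correct sentence beside a wrong one leaves the contradiction in place.

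Second, the sample-size text speaks of a null hypothesis that the mean is 71.27, which might suggest a test against control. The same software output names 51.87 as the value tested, and its power figure reproduces only on that basis.

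Third, the conflict is rare, about 2.5%, if the true mean is the assumed 71.27, and the window is wide because the margin is wide. This stands, and it limits the severity. The larger probabilities apply only if the device is truly below the benchmark, but that is the case in which the wording of the conclusion matters.

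Fourth, the < Control label causes no numerical conflict at n = 35 to 80 with SD 19.40. That also stands; the objection to it is logical.

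**Conclusion.** The concern holds. The test and hypotheses are coherent; the conclusion labels are not what the test can show. At SD 19.40 with the t-test, the ≥ Control label is available from 57.4 (n = 35) or 55.5 (n = 80). It coincides with a 95% interval wholly below 71.27 for observed means of 57.4–64.6 or 55.5–67.0. Using the benchmark's lower confidence bound of 67.03 instead, these windows shrink to 57.4–60.4 and 55.5–62.7.

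The figures treat 71.27 as fixed, as the plan does, and rest on the assumed range for 24-month n. This should be fixed before the primary endpoint is reported; it does not invalidate the design.

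**What to change.** In Protocol 11.3.2 and SAP 3.1.1:

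1. Replace the labels. For p ≤ α: non-inferiority within 19.40 points shown (24-month mean, or median if the sign test is used, above 51.87). For p > α: non-inferiority not shown.
2. Remove equal or better as the meaning of non-inferiority, here and in Protocol Table 2 and SAP Table 3.2, and remove the ≥ Benchmark path wording in those two tables.
3. State θ = 19.40 and call 51.87 the threshold throughout, including the sample-size tables and SAP 6.6.
4. Report the mean difference from 71.27 with its 95% confidence interval beside the primary test, say that 71.27 is taken as fixed, and print the benchmark's own interval (67.03 to 75.51) next to it. If the sign test is used, make clear that the interval describes the mean while the test concerns the median.
5. Make no equal-or-better claim from this test.

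The cost is wording in two documents and one reported difference that follows from an interval already planned. No extra subjects are needed. The sponsor gives up a more favourable claim that the test cannot support.

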p-value > $\alpha$ (0.05)	Fail to reject null hypothesis ( $H_0$ )	ReUnion RSA System < Control (Benchmark) Insufficient evidence to reject the null hypothesis ( $H_0: A - B < -\theta$ ) at the pre-determined significance level of 5%.
p-value $\leq \alpha$ (0.05)	Reject null hypothesis ( $H_1$ )	ReUnion RSA System $\geq$ Control (Benchmark) Sufficient evidence to reject the null hypothesis ( $H_0: A - B < -\theta$ ) at the pre-determined significance level of 5%.

Table 3.1.1: Research Goal and Hypothesis (Primary Endpoint)

To test non-inferiority, the 24 months mean ASES Shoulder Score result of the ReUnion RSA System group will be compared to the mean estimate of the control group (71.27 points).

To be able to identify an acceptable difference or zone of indifference ( $-\theta$ ), the pooled standard deviation of the ASES Shoulder Score result at 24 months postoperative in the control group (Benchmark) was used as lower limit (pooled standard deviation of control is 19.40 points). The lower maximum acceptable difference ( $-\theta$ ) is 51.87 points (mean of control -  $\theta$  or 71.27 – 19.40 = 51.87 points).

Based on the underlying distribution of the data and the result of the normality assessment, either the parametric one-sample t-test or the non-parametric one-sample sign test will be used to compare the 24 months postoperative ASES Shoulder Score results of the ReUnion RSA System against the value of 51.87 points.

The analysis of the primary endpoint / objective will be conducted when all subjects have completed the 24 months postoperative visit including the ASES Shoulder Score.

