## 6.6. ANALYSIS OF CI ENDPOINTS

Evaluation Variable / Question	Level of Measurement	Analysis Plan					
Endpoints – Primary Endpoint							
Use variable Total ASES Score 24 Months [points]:							
Based on the underlying distribution of the data and the result of the normality assessment, either the parametric one-sample t-test or the non-parametric one-sample sign test will be used to compare the 24 months postoperative ASES Shoulder Score results of the ReUnion RSA group against the lower maximum acceptable difference ( $-\theta$ ) of 51.87 points.							
The analysis of the primary endpoint will be part of the final report.							

Table 6.6.1: Endpoints – Primary Endpoint Tables List

Evaluation Variable / Question	Level of Measurement	Recode and Analysis Plan	Inclusion		
Adverse Events – Time to (earliest) Device-Related Adverse Event / Incident			IR	FR	N/A
Creation of variable Difference between Date of Surgery [dd.mm.yyyy] and Date of First Device Related Adverse Event [dd.mm.yyyy] in [ ] days [ ] (Variable(s): VISITDT; AEONSTD)	Quantitative, ratio	Case summary with number and percentage of valid cases/values, missing cases/values (if any) and total cases/values. Mean, median, interquartile range, maximum, minimum, standard deviation, 95% confidence interval for mean, Shapiro-Wilk Test.		X	
Creation of variable Difference between Date of Surgery [dd.mm.yyyy] and Date of “most recent” Visit [dd.mm.yyyy] in [ ] days [ ] (Variable(s): VISITDT)	Quantitative, ratio	N/A (Analyzed above), used for survivorship		X	
Create new variable “Grouping variable – First Device Related Adverse Event” (Variable(s): AEONSTD)	Qualitative, nominal	- censored = survivors - events = first (earliest) Device Related Adverse Event		X	

Create new variable “Combined Time – First Device Related Adverse Event” (Variable(s): AEONSTDT)	Quantitative, ratio	- Use time between surgery and “most recent” visit for surviving subjects - Use time between surgery and first device related adverse event for subjects with device related adverse event	X	

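### The non-inferiority margin is the average patient-level SD (19.40 points), with no clinical reason given; passing the resulting limit of 51.87 cannot support an equal-or-better conclusion

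*Protocol*

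**What the plan says.** Protocol 11.3.2 and SAP 3.1.1 set up a one-sample non-inferiority comparison of the 24-month ASES score with a literature benchmark of 71.27. For the zone of indifference, "the pooled standard deviation of the ASES Shoulder Score result at 24 months post-operative in the control group (Benchmark) was used as lower limit", and "pooled standard deviation of control is 19.40 points". The score is then tested, by one-sample t-test or sign test, "against the value of 51.87 points", at one-sided 5%. Both documents define non-inferiority as a result equal to or better than control, and their decision tables translate p ≤ 0.05 into device ≥ control.

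The margin and the limit share one symbol. Protocol 11.3.2 and SAP 3.1.1 call 51.87 −θ, while the same lines derive it as the control mean less θ, which makes θ 19.40. The opening of Protocol section 11 attaches the symbol to 51.87 as well. The sample-size tables (Protocol Table 2, SAP Table 3.2) list 51.87 as the non-inferiority margin. SAP Table 6.6.1 tests "against the lower maximum acceptable difference", again 51.87.

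The power statement assumes that the sampled population "has a mean of 71.27 points with a standard deviation of 19.40 points".

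**The concern.** A margin states how much worse the mean may be and still be acceptable. The SD of individual scores describes how far patients differ from one another and does not answer that question. Used as a margin, it loosens the test as patients within the literature arms become more variable. Neither document offers a minimal important difference, a preserved-effect argument or any other clinical basis for 19.40.

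The primary conclusion depends on this number. The protocol says the study supports safety and performance under the EU MDR, so a positive result will be used as evidence. If a device well below most of the benchmark can pass, the equal-or-better wording claims more than the test shows.

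**Working it through.** **Inputs.** 25 arm means and 15 arm SDs (Protocol Table 2, SAP Table 3.2); benchmark mean 71.27, SD 19.40, limit 51.87; one-sided α = 0.05 (Protocol 11.3.2); enrolment 80; overall drop-out 56%.

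**1. The plan's own figures.** The unweighted average of the 25 arm means is 71.268 (between-arm SD 10.270). The unweighted average of the 15 reported SDs is 19.400. So 71.27 − 19.40 = 51.87, as printed. For power, the noncentrality is (71.27 − 51.87)/19.40 × √10 = 3.162. With 9 degrees of freedom and a two-sided 5% t-test this gives 80.3%, which matches. The calculation therefore treats 51.87 as the constant tested against.

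**2. Where the limit lies.** The lowest arm means are 40.8, 55, 58.6, 65.0 and 65.0.
- Only 40.8 is below 51.87, so 24 of 25 arms are above it.
- 67.03 − 51.87 = 15.16 points below the printed lower confidence bound.
- 19.40/10.27 = 1.9 between-arm SDs below the benchmark mean.

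**3. Evaluable numbers.** 80 × (1 − 0.56) = 35.2, taken as 35. With an assumed 25% loss, 80 × 0.75 = 60. With no loss, 80. The documents give no 24-month drop-out rate.

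**4. Lowest observed mean that passes** (sample SD 19.40): 51.87 + t(0.95; n−1) × 19.40/√n.
- n = 35: 51.87 + 1.691 × 3.279 = 57.4
- n = 60: 51.87 + 1.671 × 2.505 = 56.1
- n = 80: 51.87 + 1.664 × 2.169 = 55.5

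**5. Probability of passing at a true mean of 60** (between the 58.6 and 65.0 arms, so below 22 of 25). For the t-test the noncentrality is (60 − 51.87)/19.40 × √n. For the sign test, with normal scores assumed, P(score > 51.87) = Φ(8.13/19.40) = 0.662.

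| Evaluable n | Noncentrality | t-test passes | Scores above 51.87 needed | Sign test passes |
|---|---|---|---|---|
| 35 | 2.479 | 78% | 23 | 60% |
| 60 | 3.246 | 94% | 37 | 81% |
| 80 | 3.748 | 98% | 48 | 90% |

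Across the band of true means that lie below 22 arms (58.7 to 64.9), the t-test passes with probability 65% to 99% at n = 35 and 93% to about 100% at n = 80.

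**6. Does sample size force the wide margin?** At a true mean of 71.27, power against 51.87 exceeds 99.9% at n = 35 and at n = 80. For illustration, take a 10-point margin, so the limit is 61.27:

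| True mean | n = 35 | n = 80 |
|---|---|---|
| 71.27 | 91% | 99.8% |
| 68 | 64% | 92% |
| 60 | 2% | 1% |

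The pooled test has room for a narrower margin, but that room shrinks if the true mean is a few points below the benchmark.

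**The case against.** Several points on the other side are sound.

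- **Chance of passing.** A reader might infer that a poor device would pass almost regardless. The documents do not support that. The probability depends on how many subjects are evaluable at 24 months and on which test is used, and at 35 evaluable with the sign test it is 60%. On the other hand, the 56% drop-out is described as overall and rests on a follow-up of at least 10 years, so 35 is probably pessimistic for a 24-month endpoint.
- **Labelling.** A reader might take −θ = 51.87 literally and conclude that the hypothesis demands a mean of 71.27 + 51.87 = 123.14. Protocol 11.3.2 prints both the subtraction and the value tested against, so the decision rule is clear. This is a labelling error that does not alter the result.
- **Literature noise.** Only within-arm spread enters 19.40. Disagreement between studies (SD 10.27) does not.
- **Visibility.** The device is already cleared, and the 24-month mean with its 95% CI will be reported, so a mean near 58 could be seen beside 71.27. That reduces the harm but does not correct the stated conclusion.
- **Case mix and timing.** The six arms that the SAP labels as revision of failed arthroplasty average (71.8 + 66.2 + 65.0 + 40.8 + 65.3 + 65.6)/6 = 62.45, and the SAP does not fix the indication mix, so a true mean below 71.27 is plausible. The study is unblinded and total ASES scores appear in the annual reports, so a margin narrowed after scores have been seen would be post hoc. Both points limit the remedy; neither justifies 19.40.

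**Conclusion.** The concern holds. The margin is an average SD of individual scores with no clinical justification. The single primary test against 51.87 can show only that the mean is not 19.40 or more points below 71.27. It cannot show that the device equals or exceeds the benchmark, which is how both documents read a significant result. The mislabelling of 51.87 is a separate, smaller error.

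The 78%, 94% and 98% for a true mean of 60 rest on SD 19.40, the one-sided 5% t-test and 35, 60 and 80 evaluable subjects. With the limit kept at 51.87 and the SD varied over about the printed interval for the average SD (17.7 to 21.1), the figure runs from 85% down to 72% at n = 35 and from 99% down to 96% at n = 80.

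A reader might also infer that 10 points is the correct margin. The documents contain no clinical figure, so they support asking for a justified margin but not a particular value.

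**What to change.** 1. In the opening of Protocol section 11, Protocol Table 2, Protocol 11.3.2, SAP 3.1.1, SAP Table 3.2 and SAP Table 6.6.1, define θ as the margin and the limit as 71.27 − θ. Stop calling 51.87 −θ or the non-inferiority margin.
2. Replace the SD-based margin with a fixed number of ASES points, state the clinical reason, and date and fix it without reference to 24-month study scores. Restate power for that margin by evaluable n and for true means below 71.27.
3. In Protocol 11.3.2 and SAP 3.1.1, replace the equal-or-better and device ≥ control conclusions with: mean not worse than the benchmark by more than θ points. Report the 24-month mean and its confidence interval beside 71.27.

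If 24-month scores have already been seen, keep 51.87 as the pre-specified test, label any tighter margin post hoc, and still make changes 1 and 3.

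The cost is protocol and SAP wording and a revised power statement, with no additional patients. The price is a stricter test with lower stated power: under the 10-point illustration at n = 35, from above 99.9% to 91% if the true mean is 71.27, and to 64% if it is 68.
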